10.0 Local Number of Participants

Three hundred and fifty participants are needed for the study. Anticipating a 15% attrition rate, a total of 400 of participants will be enrolled into the study. We expect about 300 non-smokers and about 100 smokers.

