Measurements: For the comparison between the two treatment groups, we will consider measurements excluding the baseline observation. Measurements will be taken from each subject in the two supplementation sequences as seen in the following diagram:

Group 1: Period #1 (watercress; A1) – washout – Period #2 (placebo; B2)

Group 2: Period #1 (placebo; B1) – washout – Period #2 (watercress A2)

The letter is used to denote supplementation (A for watercress and B for placebo) and the number, 1 or 2, denotes the period. We will assume, in the formulation of statistical models, that the measurements A1, A2, B1, and B2 are “normally distributed” in log-scale. These letters can represent one of our outcome variables: urinary mercapturic acid levels of specific toxicants (e.g. benzene, acrolein, crotonaldehyde, propylene oxide, etc.) or for mercapturic acids generally, or DNA adducts of acrolein.

Main Outcome Variables: Our data analysis will be based on the following “outcome variables”:

$$X1 = B2 - A1; \text{ and } X2 = B1 - A2.$$

This subtraction will cancel the “within-sequence” effects of all subject-specific factors, leaving only two to be modeled and analyzed: the Treatment (or Supplementation) effect and the Period (or Order) effect. The measurements will result in two independent samples. Each will have the same sample size if there are no dropouts or missing data. Otherwise the number of subjects for each group of measurements (i.e., X1 and X2) will differ if there are dropouts and missing data.

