We would obtain values of X1 or X2, which is a log of "ratio" for each subject in each of the two groups with different supplementation order, it's (watercress/placebo) for group 1 and (placebo/watercress) for group 2. We'll then compute the averages of these log ratios, i.e \bar{x}_1 and \bar{x}_2 . We will do this calculation separately for the double null group ($\hat{\alpha}_{nn}$), and single null group ($\hat{\alpha}_{np}$). We will compare this average ratio with the average ratio of the double positive group ($\hat{\alpha}_{pp}$). With the double nulls being about 15% of the population, *GSTM1* single nulls (45%) and *GSTT1* single nulls (23%), we expect to see 60 double nulls, 180 *GSTM1* single nulls, 92 *GSTT1* single nulls, and 68 double positive individuals. If there is no influence of *GSTM1* or *GSTT1*, the effect of watercress supplementation would be the same between the double null and the double positive group or between the single null and the double positive group. We will test for the significance of the genotypic effect by using a two-sample t test.

PROTOCOL TITLE: Watercress in Detoxification of Environmental Toxicants and

Carcinogens

VERSION DATE: July 23, 2020

In order to estimate the power for that comparison, we need information on the variability of mercapturic acid levels within and between subjects. We will compute the variances of each of these genotypic groups separately and then obtain a pooled variance estimate to compute our pooled t test statistic. Based on our previous work, we used an intra-subject CV of 0.4 and an inter-subject CV of 0.6, which translates to a pooled standard deviation of 0.657. According to Table 3, the percentage difference between the Placebo and PEITC groups with the double null genotypes varied from 29.8% to 95.4%, whereas the percentage difference for the double positive genotypes varied from 4% to 7%. In general, we will have 80% power to detect a difference of 35% between the double null and double positive group and given the range of difference between these two groups in Table 3, we expect to have good power to study this interaction between watercress and *GSTM1* or *GSTT1* genotypes.

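### The log ratio X1 has opposite signs in two adjoining paragraphs, and no rule combines the sequence means, so one reading of the genotype t-test removes the watercress effect

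*Combined protocol and SAP*

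**What the plan says.** All of this is in section 15.0 of the combined protocol and SAP.

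- The Measurements paragraph sets A = watercress and B = placebo, with 1 or 2 for the period. Group 1 gives A1 then B2; group 2 gives B1 then A2. Values are treated as normal on the log scale.
- Main Outcome Variables defines X1 = B2 - A1 and X2 = B1 - A2. It says the subtraction cancels the within-sequence "effects of all subject-specific factors, leaving only two to be modeled and analyzed": treatment and period.
- The next paragraph calls X1 or X2 the log of a ratio and gives its direction as "watercress/placebo) for group 1 and (placebo/watercress) for group 2". It will "compute the averages of these log ratios" as x̄1 and x̄2, repeat this by genotype to obtain one α̂ each, and then: "We will compare this average ratio with the average ratio of the double positive group". The null hypothesis is that "the effect of watercress supplementation would be the same between the double null and the double positive group", tested by a two-sample t-test.
- For the variance: "We will compute the variances of each of these genotypic groups separately and then obtain a pooled variance estimate". The SD comes from intra- and inter-subject CVs of 0.4 and 0.6, "which translates to a pooled standard deviation of 0.657". Stated power is 80% for a 35% difference between double nulls and double positives.
- The same analysis is repeated in smokers and non-smokers. The Multivariate Regression Analysis paragraph makes the mixed model a supplement to this t-test.

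**The concern.** By the displayed formulas, X1 and X2 are both placebo over watercress. By the sentence that follows, X2 keeps that direction and X1 is turned round.

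Each version is a coherent crossover convention, but each needs a different combining rule. The formulas are treatment contrasts in both groups, so the two sequence means must be averaged. The ratio wording is period 1 minus period 2 in both groups, so the means must be half-differenced. The plan prints no expression for α̂; its only combining language is about averages.

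The ratio wording joined to averaging estimates the period difference, not the watercress effect that the paragraph says it compares. This is the only test with a stated power, and it serves Specific Aim 3, on which section 15.0 says it focuses.

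**Working it through.** **1. The plan's own power.** Inputs: 350 completers (section 10.0: "Three hundred and fifty participants are needed for the study"); 15% double nulls and 68/400 = 17% double positives (section 15.0); SD 0.657; two-sided alpha 0.05 (not stated, assumed); 35% read as 0.35 on the log scale.

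- Group sizes: 350 × 0.15 = 52.5 and 350 × 0.17 = 59.5.
- Standard error: 0.657 × √(1/52.5 + 1/59.5) = 0.1244.
- 0.35 / 0.1244 = 2.81. Power is 80.3% by the normal approximation and 79.6% by the noncentral t.

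The stated 80% is reproduced on this basis. It presumes an estimator that keeps the watercress effect.

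**2. What each reading estimates.** Let τ be the watercress effect, π1 and π2 the period effects, and d = π1 - π2, with no carryover. Subject effects cancel in every row.

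| Definition | E[X1] | E[X2] | Average (x̄1 + x̄2)/2 | Half-difference (x̄1 - x̄2)/2 |
|---|---|---|---|---|
| Displayed formulas | -τ - d | -τ + d | -τ (valid) | -d (τ lost) |
| Ratio wording | τ + d | -τ + d | d (τ lost) | τ (valid) |

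Two of the four combinations keep the effect and two remove it. If subjects are simply pooled across sequences, the removal is complete only when the sequences are balanced within genotype.

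As an example, Table 3 gives SPMA increases of 95.4% in double nulls and 6.1% in double positives: τ = ln 1.954 = 0.670 and ln 1.061 = 0.059. A valid reading targets 0.670 - 0.059 = 0.611. A cancelling reading gives d in both genotypes (or -d in both), so the contrast is zero.

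**3. Rejection rates.** The valid column is the noncentral t at 52.5 vs 59.5. The cancelling column is simulated at 52 vs 60 with balanced sequences, d = 0 and one variance per genotype across both sequences, as the plan describes.

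| True log difference | Valid | Cancelling |
|---|---|---|
| 0.35 | 79.6% | 3.7% |
| ln 1.35 = 0.300 | 66.7% | 4.0% |
| SPMA, ln(1.954/1.061) = 0.611 | 99.8% | 1.7% |
| 3-HPMA, ln(1.327/1.070) = 0.215 | 40.3% | 3.9% |
| HMPMA, ln(1.298/0.960) = 0.302 | 67.1% | 4.2% |

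The simulated valid figure at 0.35 is 79.4%. The cancelling rates fall below 5% because a per-genotype variance that mixes +τ and -τ is inflated. They move by a few tenths of a point with the effect assumed in double positives. With a variance taken within sequence-by-genotype cells, the two cancelling readings reject at 4.9% and 5.0%, the nominal level.

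**4. Sensitivity at 0.35.** The valid reading gives 84.7% on the enrolled counts (60 vs 68) and 78.5% on 340 completers (400 less 15%). With SD = √(2 ln 1.16) = 0.545, which uses the intra-subject CV alone and one value per period, it gives 92.0%. The cancelling reading stays between about 3% and 4%.

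**The case against.** - **The brackets may only describe treatment order.** They match the sequence diagram: group 1 watercress then placebo, group 2 the reverse. But the sentence is defining the log of a ratio and uses slashes, so this reading does not fit its words. It would also leave α̂ without a formula.
- **The displayed formulas govern.** The plan says its analysis is based on them, and with a plain average they give a valid estimate. This stands, and it is why the harm is conditional.
- **A half-difference appears nowhere in section 15.0.** True. The only cancelling route with support in the text is the ratio wording averaged, so the four combinations should not be read as equally likely.
- **The power figures inherit a doubtful genotype split.** In Table 3, 38 of 82 (46%) had both genes present, and its marginal null rates of 37/82 (45%) and 19/82 (23%) equal the plan's single-null percentages. At 52.5 vs 162, valid power is 92% at 0.35 and 82% at ln 1.35. This changes the valid column; it does not restore a contrast whose expectation is zero.
- **The plan's own variance is adequate once the signs agree.** Nearly so for a small period effect: at d = 0.1 it gives 79.0% power against 79.1% with the four-cell version. It is not adequate in general, as shown under the fix.
- **Scope is limited.** Section 3.0 states the endpoint as the effect of watercress in 350 subjects, and the mixed model does not use X1 or X2. Both points are right. But the mixed model's parameter of interest is worded as treatment order by genotype, so it does not resolve the ambiguity by itself.

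**Conclusion.** The concern holds. X1 has opposite signs in two adjoining paragraphs, and nothing states how x̄1 and x̄2 become α̂. The ratio wording combined with averaging estimates the period difference and would leave the genotype test rejecting at or below its nominal level, about 4% against about 80% at a log difference of 0.35.

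Those figures assume two-sided alpha 0.05, sequences balanced within genotype, no carryover, the plan's genotype percentages, and 0.657 as the SD of each log ratio. The last is questionable, because 0.657 includes between-subject variation that the plan says subtraction removes. The cancellation itself depends on none of the power inputs.

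This is an ambiguity that should be settled before the t-test is coded, not evidence that the analysis will fail.

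**What to change.** 1. Use one orientation for both groups. Either keep the formulas and describe both ratios as placebo/watercress, or define both as log watercress minus log placebo. The sign is only a convention.
2. State α̂ = (x̄1 + x̄2)/2 for each genotype, weighting the two sequences equally, so that the period effect cancels even when dropout unbalances them.
3. Match the standard error: per genotype, variance = (s²/4)(1/n1 + 1/n2), where n1 and n2 are its numbers in the two sequences and s² is pooled within the four sequence-by-genotype cells. This replaces the variance taken per genotype across both sequences.

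Steps 2 and 3 matter when the period effect is not small. At an illustrative d = 0.3 with balanced sequences, power at 0.35 is 79.4%, against 73.2% with aligned signs and the plan's pooled variance. At the same d, with sequences split 60/40 in one genotype and 40/60 in the other, type I error is near 5% against 11.6%.

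The cost is a few lines of text, with no change to conduct or sample size. For a proportion f in one sequence, equal weighting multiplies the variance by 1/(4f(1 - f)): 1.010 at 55/45 and 1.042 at 60/40. Power at 0.35 on 350 completers goes from 79.6% to 79.2% and 78.0%.

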The results of the clinical trial of PEITC that form the basis of this proposal have been described [21]. The study was a randomized, placebo-controlled, double-blind phase II clinical trial with a crossover design. Current smokers of 10-45 cigarettes per day who were 21 years or older and in good health were enrolled. For reasons unrelated to this proposal, the subjects smoked commercial cigarettes with added [pyridine-D4]NNK during the study. After 2 weeks of adaptation to smoking these cigarettes, the smokers were randomly assigned to either the PEITC then placebo arm or the placebo then PEITC arm of the trial. During the treatment period, each subject was asked to take PEITC (10 mg in 1 ml olive oil) 4 times/day, once every 4 h, for five days (week 3 or 5), or the placebo agent (olive oil) on the same schedule (week 3 or 5). There was a one week washout period between the PEITC and placebo treatments (week 4). Twenty-four h urine samples were collected at the end of the smoking adaptation period (week 2), on 3 days (3rd, 4th, and 5th day) of each of the two treatment periods (weeks 3 and 5), and at the end of the washout period (week 4). Blood and buccal cell samples were collected at baseline, and at the end

PROTOCOL TITLE: Watercress in Detoxification of Environmental Toxicants and Carcinogens

VERSION DATE: July 23, 2020

of the smoking adaptation period, each of the two treatment periods, and the washout period. Forty-one subjects in the PEITC-placebo group and 41 subjects in the placebo-PEITC group completed the study. Their urine samples were analyzed for SPMA, 3-HPMA, and HMPMA, mercapturic acids derived from benzene, acrolein, and crotonaldehyde, respectively, using validated methods [61,62].

Table 2. Geometric means (95% confidence intervals) of baseline urinary mercapturic acid metabolites of benzene, acrolein and crotonaldehyde, in smokers separated by glutathione S-transferase (GST) M1 and T1 genotypes.

GST genotype	N ^a	Benzene SPMA (pmol/mg Cr) ^b	Acrolein 3-HPMA (nmol/mg Cr) ^b	Crotonaldehyde HMPMA (nmol/mg Cr) ^b
GSTM1				
Null	36	1.72 (1.22-2.40)	7.12 (5.98-8.48)	5.16 (4.22-6.28)
Present	45	3.10 (2.28-4.20)	6.28 (5.36-7.36)	4.28 (3.58-5.12)
P		0.014	0.309	0.186
GSTT1				
Null	19	0.80 (0.52-1.18)	7.22 (5.64-9.22)	5.26 (3.98-6.94)
Present	62	3.34 (2.68-4.18)	6.48 (5.66-7.40)	4.48 (3.86-5.22)
P		<0.001	0.459	0.338
GSTM1 & GSTT1				
Both null	12	0.44 (0.28-0.74)	8.58 (6.26-11.74)	5.76 (4.02-8.26)

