One present	31	2.84 (2.12-3.82)	6.28 (5.22-7.58)	4.82 (3.88-5.96)
Both present	38	3.56 (2.74-4.66)	6.40 (5.40-7.58)	4.22 (3.48-5.12)
P for trend		<0.001	0.244	0.130

^a One subject who did not provide a urine sample at baseline was excluded from all analyses.

^b All geometric means were adjusted for age and gender.

As shown in **Table 2**, *GSTT1* and *GSTM1* status had a strong effect on levels of SPMA from benzene, but not on levels of 3-HPMA or HMPMA from acrolein and crotonaldehyde, respectively. This is consistent with previous results [62-64].

Among all subjects, intake of PEITC significantly increased the urinary excretion of SPMA by 24.6% (P=0.002) and 3-HPMA by 15.1% (P = 0.005), but did not have a significant effect on levels of HMPMA. But as shown in **Table 3**, larger effects were observed when the subjects were classified by *GST* genotype.

Table 3. The effect of PEITC on the changes of urinary concentrations of mercapturic acid metabolites of benzene, acrolein and crotonaldehyde in smokers stratified by the *glutathione S-transferase (GST) M1* and *T1* genotype, The PEITC Intervention Study 2008-2013.

GST genotype	N	Geometric mean		% difference (95% CI)	P ^a	P for interaction ^b
		Placebo	PEITC			
GSTM1						
		Benzene SPMA (pmol/mg creatinine)				
Null	37	2.09	2.99	43.1 (18.1, 73.4)	<0.001	0.060
Present	45	3.12	3.47	11.2 (-6.5, 32.4)	0.234	
GSTT1						
		Null				
Null	19	0.83	1.45	74.2 (33.9, 126.6)	<0.001	0.006
Present	63	3.67	4.14	12.7 (-2.4, 30.4)	0.108	
GSTM1 & GSTT1						
		Both null				
Both null	12	0.74	1.45	95.4 (40.7, 171.5)	<0.001	0.009
One present	32	2.64	3.36	27.4 (4.3, 55.6)	0.020	
Both present	38	3.84	4.07	6.1 (-11.6, 27.5)	0.526	
GSTM1						
		Acrolein 3-HPMA (nmol/mg creatinine)				
Null	37	8.07	10.05	24.6 (7.9, 43.8)	0.005	0.179
Present	45	6.79	7.37	8.6 (-4.3, 23.2)	0.210	
GSTT1						
		Null				
Null	19	8.00	10.12	26.6 (5.4, 52.0)	0.022	0.320
Present	63	7.15	8.00	12.0 (-0.1, 25.6)	0.057	
GSTM1 & GSTT1						
		Both Null				
Both Null	12	9.84	13.06	32.7 (5.9, 66.2)	0.034	0.315
One present	32	6.90	8.28	20.0 (1.8, 41.3)	0.038	
Both present	38	7.04	7.53	7.0 (-6.9, 22.9)	0.347	
GSTM1						
		Crotonaldehyde HMPMA (nmol/mg creatinine)				
Null	37	5.89	6.80	15.4 (3.9, 28.1)	0.009	0.027
Present	45	4.62	4.53	-1.9 (-10.8, 7.8)	0.686	
GSTT1						
		Null				
Null	19	5.34	6.52	22.0 (5.3, 41.4)	0.010	0.031
Present	63	5.10	5.15	1.0 (-6.8, 9.5)	0.808	
GSTM1 & GSTT1						
		Both Null				

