Multivariate Regression Analysis: We will use multivariate regression analysis to supplement the t-test by pooling the data together and using each of the primary outcome variables as dependent variable, separately. In addition to the variables representing the supplementation, treatment order, and status of *GST (M1, T1)* genotypes, the list of independent variables will include socio-demographic characteristics such as gender, age, smoker vs non-smoker, baseline smoking level (cigarettes per day), and intake of dietary nutrients. We will fit a linear mixed-effect model where the dependency in the repeated measurements on each individual will be captured through a random effect. The status of *GST (M1, T1)* genotypes will be modeled as fixed-effects and we will test for the null hypothesis of no association between the genotypes and each outcome. Our primary parameter of interest will be the interaction between the treatment order (pre vs post) and the genotype groups (double null, *GSTM1* single null, *GSTT1* single null, and double positives). We will perform a t-test to assess the significance of the interaction parameter. The residual covariance structure should be selected among several candidates, i.e. autoregressive, compound symmetry, unstructured, etc., to estimate the fixed and random effects. We do not anticipate much missing data on the participants. In general, we will assume missingness at random (MAR) and the likelihood-based linear mixed effect model will provide consistent estimates of our parameters of interest in presence of MAR. The models will be assessed through their Akaike's Information Criterion and Bayesian's Information Criterion. The normality of the outcome variables will be assessed and in presence of non-normality, we will also implement Generalized Estimating Equations to study the impact of watercress and genotypes on each outcome variable. We will use the statistical software R packages nlm and gee to perform the above analysis. These packages will also provide the flexibility to fit non-linear mixed effect models to assess the impact of watercress and genotype groups.

PROTOCOL TITLE: Watercress in Detoxification of Environmental Toxicants and Carcinogens

VERSION DATE: July 23, 2020

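### Expected genotype counts use overall GSTM1-null and GSTT1-null rates as single-null rates; the protocol's own tables imply about 185 double positives and 34 GSTT1-only nulls per 400, not 68 and 92

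*Combined protocol and SAP*

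**What the plan says.** Section 15.0 (Statistical Considerations) gives the expected genotype make-up of the sample. After a double-null share of about 15% and a GSTM1 single-null share of 45%, it continues "single nulls (23%), we expect to see 60 double nulls, 180" GSTM1 single nulls, then 92 GSTT1 single nulls, "and 68 double positive individuals". No source is named for the percentages.

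Double positives are the reference group for the two-sample t tests on genotype. The same section claims "80% power to detect a difference of 35% between the double null and double positive group", without giving group sizes, alpha, sidedness or the scale of the 35%. The regression part of the section uses the same four genotype groups as levels of one factor and names as its main parameter the "interaction between the treatment order (pre vs post) and the genotype groups".

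The only genotype data in the document are Tables 2 and 3 in Section 2.0 (Preliminary Studies), from the earlier PEITC crossover trial: "Forty-one subjects in the PEITC-placebo group and 41 subjects in the placebo-PEITC group completed the study". Table 3 reports effects on the metabolites of "benzene, acrolein and crotonaldehyde in smokers stratified by the" GST genotype, with N = 82. Table 2 has N = 81, because "One subject who did not provide a urine sample at baseline was excluded from all analyses".

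**The concern.** The four expected counts add to exactly 400, and 68 arises only as the remainder after the other three are subtracted. The plan therefore treats the four groups as exclusive, as the regression factor also requires. But 15%, 45% and 23% are what Table 3 gives for both null, all GSTM1 null and all GSTT1 null. Those are overlapping totals: every double null is also a GSTM1 null and a GSTT1 null.

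If overall rates were used as single-null rates, the same 60 people sit in the 60, again in the 180 and again in the 92, and the double positives absorb the shortfall. At stake are the planned sizes of the genotype groups that Section 15.0 says it focuses on: the reference group in every contrast, and the smallest group, GSTT1-only, whose expected number decides how much can be learned about it.

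**Working it through.** **1. Reproduce the plan's figures (Section 15.0).**
- 0.15 × 400 = 60; 0.45 × 400 = 180; 0.23 × 400 = 92.
- Remainder: 400 − 60 − 180 − 92 = 68 (17%).

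**2. Compare with Table 3 (n = 82).**
- GSTM1 null 37/82 = 45.1%; GSTT1 null 19/82 = 23.2%; both null 12/82 = 14.6%. All three round to the plan's percentages.
- GSTM1-only: 37 − 12 = 25. GSTT1-only: 19 − 12 = 7.
- 25 + 7 = 32, which is the One present row; 12 + 32 + 38 = 82.
- Table 2 has the same structure: 36 − 12 = 24, 19 − 12 = 7, 24 + 7 = 31, and 12 + 31 + 38 = 81.

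**3. Consequence of reading the plan literally.** GSTM1 null overall would be 45 + 15 = 60%, GSTT1 null 23 + 15 = 38% and double positive 17%. Table 3 has 45%, 23% and 46%.

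**4. Exclusive shares and counts.** The range is the exact 95% interval for the Table 3 share, scaled to 400.

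| Group | Share (Table 3) | Stated, of 400 | Table 3, of 400 | Range, of 400 | Of 350 | Of 340 |
|---|---|---|---|---|---|---|
| Double null | 14.6% | 60 | 59 | 31–97 | 51 | 50 |
| GSTM1-only | 30.5% | 180 | 122 | 83–167 | 107 | 104 |
| GSTT1-only | 8.5% | 92 | 34 | 14–67 | 30 | 29 |
| Double positive | 46.3% | 68 | 185 | 141–231 | 162 | 158 |

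The stated 180, 92 and 68 all lie outside their ranges. Testing 38/82 against 17% gives an exact binomial p of about 7 × 10⁻¹⁰. Ratios: 185.4/68 = 2.73 and 92/34.1 = 2.69.

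Taking the plan's rounded percentages as overlapping totals gives 45 − 15 = 30%, 23 − 15 = 8% and 100 − (45 + 23 − 15) = 47%, or 60/120/32/188 of 400. The gap in double positives, 188 − 68 = 120, is the 60 double nulls counted twice too often.

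**5. Effect on the contrasts with double positives.** Inputs: SD 0.657 (Section 15.0), two-sample t test, two-sided 5% (assumed, because the plan gives no alpha), noncentral t. The noncentrality is δ / [0.657 × √(1/n₁ + 1/n₂)]. The table gives the ratio detectable with 80% power, stated split → exclusive split.

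| Contrast with double positive | N = 400 | N = 340 |
|---|---|---|
| Double null | 1.39 → 1.32 | 1.43 → 1.35 |
| GSTM1-only | 1.30 → 1.24 | 1.33 → 1.26 |
| GSTT1-only | 1.34 → 1.41 | 1.38 → 1.45 |

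Over the 95% interval for the GSTT1-only share (3.5% to 16.8%, about 12 to 57 of 340), its detectable ratio at 340 runs from 1.74 down to 1.33.

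Power for δ = 0.35 on the log scale at N = 400:
- Double null: 84.7% → 94.3%.
- GSTT1-only: 91% → 81%. At 340 on the exclusive split it is 75%, or 61% if 35% means a ratio of 1.35.

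**6. Can the plan's 80% be traced?** With 52.5 against 59.5 (the stated split of 350) and δ = 0.35, power is 79.6%. With 49.8 against 157.6 (the exclusive split of 340) and δ = ln 1.35, it is 79.9%. More than one combination gives about 80%, so the basis of the statement cannot be identified.

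**7. Completers (Section 10.0).** 400 × 0.85 = 340, not 350; 350/400 = 87.5%, which is 12.5% attrition. 350 × 1.15 = 402.5 may be how 400 arose.

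**The case against.** The plan gives its percentages as population shares and cites no source, so the link to Table 3 is an inference. That is true, but all three percentages match, and no reading of the counts as exclusive groups fits the One present and Both present rows of either table.

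The replacement counts rest on 82 smokers, whereas for this trial the protocol says "We expect about 300 non-smokers and about 100 smokers". This stands. The new figures are assumptions and need ranges.

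The strongest point is that no power claim in the plan fails. The only contrast with a stated power is double null against double positive. There the double-null count hardly moves (60 to 59), the reference group grows and power rises. If the single nulls are pooled for the t test, that contrast also improves (detectable ratio 1.28 to 1.22 at 400). GSTT1-only is a separate level only in a regression described as supplementing the t test, and at 400 it still has 81% power for a 0.35 log difference. All of this stands and limits the consequence.

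The detectable ratios also depend on an SD of 0.657, which the plan derives from both intra- and inter-subject CVs although its within-subject differences cancel subject effects. If only the intra-subject CV of 0.4 applied, with one measurement per period (an assumption), the SD of a difference would be √(2 × ln 1.16) = 0.545. GSTT1-only power on the exclusive split would then be 93% at 400 and 89% at 340. So the size of the loss is uncertain. The error in the counts, and the direction of its effect on each contrast, do not depend on the SD.

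**Conclusion.** The point holds. The expected counts of 60/180/92/68 conflict with the protocol's own Tables 2 and 3, which imply about 59/122/34/185 per 400. The evident cause is that overall null rates were used as single-null rates. Confidence is high that the stated counts conflict with the tables and moderate for the replacements, which assume that the earlier trial's genotype mix carries over to a mostly non-smoking sample.

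The error does not show that the trial is underpowered: it is conservative for the double-null and GSTM1-only contrasts. It does make the expected information on GSTT1-only look better than it is, and the plan's general expectation of good power for the genotype interaction should not be read as covering that group. The stated 80% power cannot be verified as written, and nothing here shows that it rests on 60 against 68.

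This should be corrected: the figures are planned group sizes for the section's main hypothesis, and they are wrong as written.

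**What to change.** - In Section 15.0, replace the expected counts with mutually exclusive shares of about 15% double null, 30% GSTM1-only, 9% GSTT1-only and 46% double positive. State that they are assumed from the earlier trial of smokers, and give the ranges.
- Apply the shares to expected completers: about 50/104/29/158 of 340, or 51/107/30/162 of 350.
- Restate the power with group sizes, alpha, sidedness and the scale of the 35% (log units or ratio).
- Add a sentence that the GSTT1-only group is expected to be small and its contrast in the regression correspondingly less precise than the others.
- A separate, minor point in Section 10.0: give completers as 340 or attrition as 12.5%.

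The cost is a few restated figures and one caveat. No further participants are needed and the analysis is unchanged.

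### The genotype t-tests name no sequence term although X still carries the period effect, and the supplementary model's interaction is not written as supplementation by genotype

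*Combined protocol and SAP*

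**What the plan says.** All of this is in section 15.0.

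- **Main Outcome Variables.** X is defined as a difference between the two periods (X1 = B2 − A1, X2 = B1 − A2, log scale). The plan says this cancels subject-specific factors, "leaving only two to be modeled and analyzed: the Treatment (or Supplementation) effect and the Period (or Order) effect".
- **Genotype comparison.** The mean of X is computed for each sequence, separately by genotype group. Double nulls and single nulls are each compared with double positives: "We will test for the significance of the genotypic effect by using a two-sample t test". For the error term: "We will compute the variances of each of these genotypic groups separately and then obtain a pooled variance estimate". The plan does not say how the two sequence means are combined, and no sequence or period term is named. The stated power is that "we will have 80% power to detect a difference of 35% between the double null and double positive group".
- **Multivariate Regression Analysis.** A linear mixed model supplements the t-tests. Its covariates include supplementation, treatment order and genotype. The main parameter is the interaction of treatment order, glossed as pre versus post, with four genotype groups. The decision rule is: "We will perform a t-test to assess the significance of the interaction parameter".

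**The concern.** The plan recognises that X contains a period effect and then describes a lead genotype test with no place for it. If the two sequences are pooled within a genotype group, the period shift enters the variance as noise that a sequence term would remove. Genotype cannot be balanced at randomisation, because section 5.0 defers blood collection, so the sequences may also split unevenly within a small genotype group and shift its mean.

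The mixed model does not clearly repair this. It is supplementary. If treatment order means sequence, a sequence main effect in a model of individual measurements does not remove a within-subject period effect. Treatment order by genotype is also not the question in the hypothesis, which is whether the watercress effect differs by genotype.

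At stake is avoidable loss of power for the genotype question, mainly for acrolein and crotonaldehyde, and uncertainty about which coefficient answers it.

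**Working it through.** **The plan's own figure.** Inputs: 350 evaluable (section 10.0); 17% double positive and 15% double null (68 and 60 of 400), so 59.5 and 52.5; SD 0.657; difference 0.35 read as log units; two-sided 5%. The last two readings are assumptions, because the plan states neither.

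SE = 0.657 × √(1/59.5 + 1/52.5) = 0.1244. 0.35/0.1244 = 2.813. Power = Φ(2.813 − 1.960) = 0.803. The stated 80% reproduces with no period effect in the error.

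**Where the period effect goes.** Let τ be the placebo-minus-watercress effect and π the period 2 minus period 1 shift. Watercress first: B2 − A1 = τ + π. Placebo first: B1 − A2 = τ − π. With equal sequences pooled within a genotype group, the variance of X is σ² + π². With a fraction q in the first sequence, the group mean moves by (2q − 1)π. Illustration: 51 double nulls split 29 to 22, with π = 0.2, give (7/51) × 0.2 = 0.027 log units.

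**Loss on the plan's own inputs.** Replacing 0.657 by √(0.657² + π²) gives power of 0.794, 0.768 and 0.726 at π = 0.1, 0.2 and 0.3. A 5-point loss needs π of about 0.24.

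**Loss with Table 3 effects.** Inputs:

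- N = 400 × 0.85 = 340.
- SD of X = √(2 ln(1 + 0.4²)) = 0.545. This uses only the intra-subject part of "an intra-subject CV of 0.4 and an inter-subject CV of 0.6", since the between-subject part cancels in X, and one measurement per period.
- Acrolein contrast ln(1.327/1.070) = 0.215; crotonaldehyde contrast ln(1.298/0.960) = 0.302.
- Double positive and double null numbers: Table 3 mix 340 × 38/82 = 157.6 and 340 × 12/82 = 49.8; plan's counts 57.8 and 51.0.
- Noncentral t, ncp = contrast / [√(0.545² + π²) × √(1/n₀ + 1/n₂)], two-sided 5%.

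| Double null v double positive | π = 0 | 0.1 | 0.2 | 0.3 |
|---|---|---|---|---|
| Acrolein, Table 3 mix | 68% | 66% | 62% | 56% |
| Acrolein, plan's counts | 53% | 52% | 48% | 43% |
| Crotonaldehyde, Table 3 mix | 92% | 91% | 89% | 84% |
| Crotonaldehyde, plan's counts | 82% | 80% | 77% | 71% |

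Benzene stays at about 100% throughout. A sequence term returns each row to about its π = 0 value. The shifts of 0.1, 0.2 and 0.3 log units are ratios of 1.11, 1.22 and 1.35.

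**The mixed-model interaction.** A two-level factor crossed with four genotype groups gives 1 × (4 − 1) = 3 coefficients. Each has its own t-test. The text speaks of a single parameter and does not say which one leads.

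**What a trend over null genes (0, 1, 2) adds.** Slope information Sxx is compared with 4/(1/n₀ + 1/n₂), its equivalent for the two-group contrast. At the plan's counts these are 108.7 and 108.4: the mean count is 0.98, so the 68% single nulls sit at the centre and add almost nothing. Acrolein power is 53.1% (t-test) against 53.9% (trend), and crotonaldehyde 81.5% against 81.5%. With the Table 3 mix they are 173.1 and 151.3, and power rises from 68% to 75% for acrolein and from about 92% to 94% (1.5 points) for crotonaldehyde, both at π = 0. Benzene single nulls lie only ln(1.274/1.061)/ln(1.954/1.061) = 0.30 of the way up. With that shape and the plan's 0.35 difference, SD, counts and 350 evaluable, the trend gives 79.0% against 80.3%.

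**The case against.** The strongest defence is that the text is loose rather than wrong. The plan computes the two sequence means separately. Averaging them within genotype and using a within-sequence variance would remove the period effect. That reading is open, so the documents do not establish that the error term contains the period effect. But the sentence on variance speaks of genotype groups, and nothing says how the sequence means are combined. The text needs settling either way.

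The period sizes are assumptions, and at 0.1 log units the loss is only 1 to 1.5 points. That stands. A reader might also infer that the t-tests are invalid or biased. They are not: under randomisation a sequence imbalance is chance error, and the cost is precision.

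A reader might infer from the rising effects in Table 3 that a gene-count trend is more powerful at no cost and should become the main test. The documents do not support this. The gain is nil at the plan's counts, and the trend assumes equal steps and equal genes. The stated hypothesis concerns subjects null for either gene or both, which the planned contrasts address, including single null versus double positive. The gradient rests on 12 double nulls, all smokers given pure PEITC. The trend P value in Table 2 concerns baseline levels, while Table 3 reports interaction tests for the treatment effect.

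Finally, it would overstate matters to say that the mixed model cannot be run, or to charge the plan with the power of a three-degree-of-freedom omnibus test. The plan names no such test.

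**Conclusion.** The point holds as one of specification with a modest cost in power. The plan says period must be modelled, yet its lead genotype test names no sequence term and takes its variance by genotype group. On that reading, the loss across acrolein and crotonaldehyde is about 1 to 1.5 points at a shift of 0.1 log units, 3 to 5.5 at 0.2 and 8 to 11 at 0.3, and nil for benzene. These figures rest on an assumed period shift, 340 evaluable, one measurement per period, two-sided 5% and Table 3 effects carrying over to watercress. With no period effect there is no loss.

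The mixed-model wording is a defect whatever the period effect: the interaction named there is not supplementation by genotype, and no lead coefficient is identified among three. The evidence supports a gene-count trend only as an optional secondary test.

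**What to change.** **Genotype comparison.** Sign X the same way in both sequences and say so: the two formulas are both placebo minus watercress, but the later text describes opposite ratios for the two groups. Take double null versus double positive and single null versus double positive from one linear model of X on sequence and genotype group, with the residual variance taken within sequence and genotype. In this model the sequence term absorbs the period effect.

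**Mixed model.** Replace the interaction with supplementation by genotype group, include period as a fixed effect, and name double null versus double positive as the lead contrast on one degree of freedom.

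**Optional.** Add a one-degree-of-freedom trend over the number of null genes as a secondary test, with a check for departure from trend. Keep the planned contrasts in the lead.

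The cost is a few sentences in section 15.0. No extra participants, visits or data are needed, and the sequence term uses one degree of freedom.
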